Demographics and Other Covariates Measured at Baseline. We will measure patients' baseline Sociodemographic and Pain Characteristics that have been shown to be associated with treatment outcomes, e.g., age, gender, education level, racial/ethnic background, marital status, occupational status, pain duration, and number and location of pain sites. We also will gather data on participants' level of health literacy.⁷⁹ Pain Classification will be derived through a systematic evaluation of each enrolled participant's EMR using an assessment tool based on clinical guidelines for diagnosing and treating back pain.¹ Pain classes will include non-specific back pain, back pain with a radicular component, or back pain associated with other specific spinal causes. A nurse practitioner, who is supported by the West Haven COIN and who has been trained to use this tool and is using it in our trial IIR 09-058, will conduct the assessment. She will be supervised by a pain medicine physician ([name]) who will review ten percent of the classification ratings for accuracy and provide corrective feedback if necessary. Psychiatric and Substance Abuse Comorbidities will be measured using medical record diagnoses and mental health encounters. Additional self-report information will be collected using subscales of the Mini International Neuropsychiatric Interview (MINI)⁶¹ related to mood and substance abuse disorders. Pain Medication Use will be assessed through patient survey and a review of computerized pharmacy records. Pain medication will be coded as non-steroidal anti-inflammatory, non-narcotic analgesics, narcotic analgesics, and benzodiazepines and other sedative/hypnotics. For each category, we will document post-treatment whether patients have experienced an increase, no change, or decrease in their medication use. Distance from VA will be calculated and used as a measure of geographic access. The Pain Catastrophizing Scale is a 13-item self-report scale that examines thoughts and feelings people may experience when they are in pain including rumination, magnification, and helplessness.⁸⁰ Finally, Pain-related Fear will be measured using the Tampa Scale of Kinesiophobia-revised (TSK-R), which has two subscales (Fear of Harm/Activity Avoidance and Pathophysiological Beliefs) and has been shown to be sensitive to treatment-related change.

D.8 Sample Size and Power Calculation

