Our primary outcome analyses are consistent with the CONSORT Statement on Reporting of Noninferiority and Equivalence Randomized Trials.⁸¹ The sample size was calculated using the Non-Inferiority Test module available in the statistical software PASS 2008. The calculation was reviewed by the study statistician, [name]. To ensure that the AI-CBT program retains a clinically acceptable effect, the non-inferiority margin was set at 2 points on the Roland Morris Disability Questionnaire (RMDQ).⁷⁴ A two point difference (or difference in reduction) in the RMDQ is considered to be a minimally clinically significant effect.⁸² The power calculation was based on a significance level of 0.025, with a power of 90%, when postulating a true difference in group means of 0 and a standard deviation of the outcome of 4.5 in both groups. Specifically, if we denote by D the true difference in mean RMDQ scores (at 12 weeks) between the

AI-CBT and standard CBT groups, with the non-inferiority margin set at 2, we plan on testing the null hypothesis $H_0: D \geq 2$ versus the alternative hypothesis $H_1: D < 2$, which amounts to a one-sided, two-sample t-test. Thus, if the null hypothesis is rejected, it can be concluded that AI-CBT is non-inferior to CBT. We will test this hypothesis at a one-sided .025 significance level based on a confidence level where we will reject the null hypothesis when the upper bound of the two-sided 95% confidence interval for D is less than 2. To ensure that the AI-CBT algorithm has as much information as possible to learn quickly how best to tailor patients' course of therapy, we will disproportionately randomize patients to the AI-CBT group in an allocation ratio of 1.37:1 for the AI-CBT: standard CBT groups, respectively. Assuming this ratio, we will have 90% power to detect non-inferiority with a total sample size of 221 patients, or 128:93. To account for a 20% drop-out rate in both groups, we will enroll 278 patients (160 in the AI-CBT group, 118 in CBT group).

D.9 Analysis

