Analysis of Endpoints (addressing Specific Aim 1). We will test for non-inferiority of AI-CBT compared to standard telephone CBT at 12 weeks by comparing the upper limit of the two-sided 95% confidence interval for the difference in the mean RMDQ scores, calculated as AI-CBT minus standard CBT, to the pre-set non-inferiority margin of 2 points in RMDQ and will conclude that AI-CBT is non-inferior if the upper limit is less than 2. Because intent-to-treat analysis can raise the risk of type I error in a non-inferiority trial,⁸¹ we will conduct both a per protocol and intent-to-treat analysis. The "per protocol" group assignment will be defined as completing four or more CBT sessions (either IVR or "live" sessions); however, we will revisit this definition with the Expert Panel prior to the start of the trial. We will declare AI-CBT non-inferior to standard CBT only if AI-CBT is shown to be non-inferior using both the intention-to-treat and per-protocol analysis sets. We expect that RMDQ scores will be normally distributed. If not, we will use transformations to achieve normality. We also will develop a two-level linear mixed-effects model that uses RMDQ follow-up scores at both assessment times (three and six months) as the dependent variables; treatment group, time and the treatment by time interaction as categorical explanatory variables; and baseline RMDQ score as a continuous covariate. If this model shows no significant time by group effect, we can drop the interaction term and test for the time-averaged non-inferiority of AI-CBT compared to standard CBT between 3 and 6 months. This model will also allow for adjustment for design-related factors (e.g., site and age). An unstructured variance-covariance matrix will be used to model the error variance. Secondary outcomes including pain intensity, emotional functioning, global perception of change, and quality of life will be analyzed in a manner similar to that used for the primary outcome. Analyses of all other outcomes will be conducted on an intent-to-treat basis.

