Preplanned Subgroup Analysis. Because AI-CBT will continue to learn patterns in patients' experience throughout the intervention period, we hypothesize that the second 50% of patients randomized will show an even larger difference in clinician time than the first 50%, while still demonstrating non-inferiority in pain-related outcomes. Differences in pain related functioning and in clinician treatment time across treatment groups will be tested in this subgroup analysis after stratifying the sample into early versus later recruits.

Approach to Missing Data. If more than 15% of a covariate is missing, we will use multiple imputation methods based on the SAS MI Procedure. We will check if the pattern of missingness is monotonic (i.e., if patients missing data at 3 months also have missing data at 6 months) and use a Markov chain Monte Carlo method that assumes multivariate normality to impute missing values. We will impute five sets of data and combine the imputed results using the SAS MIANALYZE procedure to obtain a valid estimate of the confidence limit and treatment effect.⁸⁵ When data are missing for items within scale scores, we will use recommended imputation procedures rather than deleting patients list-wise from the analysis.

Mediators and Moderators of Intervention Effects. We will use multivariate modeling to identify the mechanisms through which the intervention achieves effects on outcomes and differential effects across subgroups.⁸⁶ Initial models will include only treatment group as the predictor. Subsequent nested models will introduce potential mediators (such as the number of completed therapist sessions), and we will evaluate changes in the relationship between experimental condition and outcomes before and after covariates are introduced. Analyses of effect moderation will focus on baseline pain severity and comorbid diagnoses using standard approaches to evaluate interactions between these covariates and patients' experimental condition.⁸⁶ Significant interactions will be interpreted by plotting regression lines for predicted outcomes of patients with high and low values of the moderator.

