We will examine the distribution of all study variables to assess extreme values, missing data, variances, skewness, and type of distribution. Preliminary analyses will examine the distributions of variables to assess deviations from normality and other deviations from assumptions of the planned statistical analyses. Outliers will be corrected. Transformations of the data will be conducted if appropriate to obtain normality of residuals.

Definitions of the Analytical Sets

Baseline Comparability, Reach, and Representativeness. We will examine baseline differences across

groups in measures of study endpoints as well as other potential prognostic indicators, such as patients' age, comorbid diagnoses, and history of pain treatment. Any differences across groups in baseline characteristics will be controlled statistically in analyses comparing outcomes. The RE-AIM framework is a methodology for systematically considering all strengths and weaknesses of an intervention in order to better guide program planning.⁸³ To evaluate reach, we will ask patients who decline study participation whether they would be willing to provide informed consent to participate in a brief survey that identifies their reasons for declining participation and the characteristics that differentiate them from enrollees.

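### At 15% or less missing, the plan states no method for a wholly missing 12-week RMDQ; above that, the trigger names only covariates, and no RMDQ analysis goes beyond missing at random

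*Combined protocol and SAP*

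**What the plan says.** The same paragraph stands in protocol D.9 (Approach to Missing Data) and in the SAP (Handling Missing Data). It opens: "If more than 15% of a covariate is missing, we will use multiple imputation methods based on the SAS MI Procedure". The plan's covariate lists, protocol D.7 and SAP Definitions of Covariates, come under the title "Demographics and Other Covariates Measured at Baseline". The paragraph then checks whether missingness is monotone, that is, "if patients missing data at 3 months also have missing data at 6 months", and states that five imputations will be combined to "obtain a valid estimate of the confidence limit and treatment effect". A separate sentence deals with missing items within a scale. Nothing deals with a wholly missing assessment when 15% or less is missing.

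Other relevant text:

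- **Sample size** (protocol D.8, SAP Sample Size Rationale): the hypothesis is one "which amounts to a one-sided, two-sample t-test", and enrolment is raised "To account for a 20% drop-out rate in both groups".
- **Baseline adjustment** (protocol D.9, SAP Definitions of the Analytical Sets): "Any differences across groups in baseline characteristics will be controlled statistically in analyses comparing outcomes".
- **Primary analysis** (Analysis of Endpoints, both documents): the upper 95% limit for the 12-week mean difference is compared with 2 points, and both the ITT and per-protocol sets must pass. Then: "We also will develop a two-level linear mixed-effects model that uses RMDQ follow-up scores at both assessment times", with baseline RMDQ as a covariate.
- **Drop-out**: unequal loss between arms is to be described with time-to-event methods. The only sensitivity analysis mentioned is for costs.

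**The concern.** The trial's claim rests on one confidence limit, and three choices that can move it are left open: whether the trigger covers the RMDQ, what is done below the trigger, and when baseline is adjusted for.

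The base for the 15% is also unstated. Counted overall, 41 missing of 278 means no imputation and 42 means imputation. Counted in the AI-CBT arm, the switch lies between 24 and 25 of 160. The SAP section on analysis sets does not say how the ITT set treats a patient with no 12-week score.

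An unadjusted comparison of completers can be biased even when data are MAR given baseline, while a model with baseline RMDQ is not. The direction is unknown in advance: losing the worse AI-CBT patients favours non-inferiority, and losing the worse controls works against it. Time-to-event analysis of drop-out can reveal unequal loss but does not correct the RMDQ estimate. Multiple imputation as described and the mixed model both assume MAR, so a reader could not tell a robust pass from a fragile one.

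**Working it through.** **1. The plan's own figures.** Inputs from protocol D.8: margin 2, SD 4.5, true difference 0, one-sided 0.025, power 90%, ratio 1.37.

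- Control n = (1 + 1/1.37) × [4.5 × (1.960 + 1.282)/2]² = 92.02, so 93. AI-CBT n = 1.37 × 93 = 127.4, so 128. The total is 221, as stated; noncentral-t power is 90.1%.
- Drop-out: 128/0.8 = 160 and 93/0.8 = 116.25, so 117, which gives the SAP's 277. The protocol has 118 and 278.

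The sample size is sound. It matters here only because the allowed loss (20%) exceeds the trigger (15%).

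**2. Trigger counts.** 0.15 × 278 = 41.7; 0.15 × 160 = 24.0.

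**3. Loss at the 15% limit, MAR given baseline.** Assumptions, not from the documents: baseline and 12-week RMDQ normal with SD 4.5 and correlation r = 0.3, 0.5 or 0.7; AI-CBT loss weighted by exp(baseline z-score); control loss random. Lost AI-CBT patients are then about 3.7 points worse at baseline than their arm's average.

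- Completers: 136 and 100. SE = 4.5 × √(1/136 + 1/100) = 0.593.
- Shift in the retained AI-CBT baseline mean = −0.15 × 3.7/0.85 = −0.653.
- Bias in the 12-week difference = r × (−0.653) = −0.20, −0.33, −0.46.
- False pass at a true difference of 2 = Φ(|bias|/0.593 − 1.96) = 5.2%, 7.9%, 11.7%.

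Simulation with 160:118 randomized agrees (Monte Carlo error about 0.2 to 0.5 percentage points). ITT test only, true difference 2, nominal 2.5%:

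| Setting | r = 0.3 | r = 0.5 | r = 0.7 |
|---|---|---|---|
| Completers t-test, 15% lost | 5.2% | 8.2% | 12.0% |
| Same test, 10% lost | 3.9% | 6.4% | 8.3% |
| Same test, half the selection strength | 4.0% | 4.9% | 6.4% |
| Same test, same pattern in both arms | 2.8% | 2.5% | 3.2% |
| Adjust if baseline p<0.05, checked in analysed patients | 3.4% | 4.1% | 4.5% |
| Adjust if baseline p<0.05, checked in all randomized | about 5% | about 7% | about 10% |
| Completers, always adjusted for baseline | 2.4% | 2.5% | 2.5% |
| Planned mixed model, 12-week contrast | 2.2% | 2.5% | 2.3% |

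The mixed-model runs also assumed a 12-week/6-month correlation of 0.7, with 70% of those lost at 12 weeks also lacking 6 months.

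**4. Pattern in controls only, true difference 0.** Power of the t-test falls from about 92% under random loss to about 86%, 80% or 73%.

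**5. Beyond MAR.** Let the tipping point be the excess of the AI-CBT delta over the control delta at which non-inferiority is lost: (2 − d − 1.96 × SE)/missing fraction, for completer difference d, with SE held fixed.

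| d | 20% missing (128:93, SE 0.613) | 15% missing (136:100, SE 0.593) |
|---|---|---|
| 0 | 3.99 | 5.59 |
| 0.25 | 2.74 | 3.92 |
| 0.50 | 1.49 | 2.25 |
| 0.75 | 0.24 | 0.59 |

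**The case against.** **The RMDQ is evidently covered.** Baseline variables have no 3- and 6-month missingness pattern, and imputing to obtain the treatment effect makes sense only for outcomes. This largely stands. A reader might infer from the word covariate that the RMDQ is never imputed at any missing fraction; the rest of the paragraph points the other way. The remedy there is one clarifying phrase. The gap at 15% or less is untouched.

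**An unadjusted completers test is not specified.** This also stands in part. The t-test is named only in the sample-size text; Analysis of Endpoints asks for a confidence interval for the mean difference and names no test. The completers t-test is one permitted reading, not the stated primary analysis.

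**Baseline differences will be controlled.** Adjusting for any difference, however small, would remove the inflation. But neither the threshold nor the population checked is given, and the table shows that both matter.

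**The one-arm pattern is strong.** Correct: the documents give no evidence for it, and a shared pattern leaves error essentially nominal.

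**The power gap to the adjusted model is not all bias.** Correct. That model's power is 94.3%, 97.3% and 99.7% under the same loss pattern, but part of its lead is precision from the covariate. The loss due to missingness is the drop from about 92%.

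**Item-level imputation and the per-protocol requirement give protection.** The first does not cover a missing assessment. The second changes the patients analysed, not the missing-data assumption, though it does make the ITT-only error rates upper bounds.

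**Conclusion.** The point holds as a cheap improvement that should be made. It is firm that at 15% or less missing no method is stated for a wholly missing 12-week RMDQ, that baseline adjustment has no operating rule, that the mixed model with baseline RMDQ is only additional, and that nothing planned for the RMDQ tests a departure from MAR. It is probable, not certain, that the imputation rule covers the RMDQ above 15%.

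The size is conditional. Under an unadjusted completers test with 15% baseline-dependent loss in AI-CBT only, ITT false non-inferiority is about 5%, 8% or 12% rather than 2.5%; with half that selection it is about 4%, 5% or 6%. The correlations and loss patterns are assumptions. A reader might infer that the trial's type I error is 5% to 12%; the documents do not support that, because they neither fix that test nor suggest that loss pattern, and the per-protocol set must also pass.

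Beyond MAR, a clear pass is robust: at a completer difference of 0, the excess delta must reach 4.0 points (20% missing) or 5.6 (15% missing). At 0.75 it is only 0.2 or 0.6, but there the upper limit is already 0.75 + 1.96 × SE, about 1.95 or 1.91.

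**What to change.** 1. State that the rule covers the RMDQ, and remove the 15% trigger for it.
2. Whatever the missing fraction, take the 12-week contrast and 95% interval, in both the ITT and per-protocol sets, from the 3- and 6-month mixed model already planned, with baseline RMDQ, site and age as covariates and the treatment-by-time interaction kept.
3. Define the ITT set as all randomized patients. State that those with neither follow-up score add no outcome information to this likelihood and are covered under MAR given the model covariates. Alternatively, use multiple imputation by arm, with baseline and both follow-ups, at any missing fraction.
4. Add one delta-adjusted multiple-imputation sensitivity analysis on all randomized patients. Vary the delta in both arms, for example over 0 to 4 points, because the direction of bias is unknown, and report the tipping points.

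Cost: SAP wording and some extra programming, with no extra patients or data. The downside is that a narrow pass may be shown to be fragile.

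### Five imputations at a planned 20% drop-out leave the deciding upper confidence limit with a seed-to-seed SD of about 0.11–0.17 RMDQ points; 50 or more would remove most of that noise at no cost

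*Combined protocol and SAP*

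**What the plan says.** Protocol D.9 (Approach to Missing Data) and the SAP (Handling Missing Data) carry the same paragraph. Multiple imputation with the SAS MI procedure starts when more than 15% of a covariate is missing, using a Markov chain Monte Carlo method under multivariate normality. Then: "We will impute five sets of data and combine the imputed results using the SAS MIANALYZE procedure to obtain a valid estimate". This pooled result supplies the treatment effect and its confidence limit. No seed, no check of Monte Carlo error and no rule for increasing the number of sets is given.

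Protocol D.8 and the SAP's Sample Size Rationale inflate enrolment: "To account for a 20% drop-out rate in both groups". The Analysis of Endpoints text in both documents compares the upper limit of the two-sided 95% interval for the 12-week RMDQ difference with the margin and "will conclude that AI-CBT is non-inferior if the upper limit is less than 2". This must hold in both the intention-to-treat and the per-protocol sets.

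**The concern.** If drop-out runs as planned, imputation is triggered and about a fifth of the 12-week scores are random draws. Averaging only five sets leaves simulation noise in two places: in the pooled difference, and in the between-imputation variance that sets the width of the interval. Both feed the single limit that is compared with 2. Near the margin, two analysts who follow the plan exactly on the same data could reach different conclusions. With no seed stated in advance, a reader could not tell whether a reported result was the first run. The interval is also a little wider on average than the data require.

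**Working it through.** **The plan's own figures.** D.8 sets the calculation at one-sided 0.025 and 90% power, "postulating a true difference in group means of 0 and a standard deviation of the outcome of 4.5 in both groups", with margin 2 and allocation 1.37:1. The normal approximation gives control n = (1 + 1/1.37) × 4.5² × (1.960 + 1.282)² / 2² ≈ 92. The t-based calculation gives 93 and 128, total 221, with exact power 0.901. The plan's 221 is reproduced. Dividing by 0.8 gives 160 and 117 (116.25 rounded up), the SAP's 277. The protocol's 278 differs by one control patient and does not matter here.

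**Inputs.** 160:117 randomised (SAP), SD 4.5, 20% of 12-week scores missing at random in each arm, m = 5. Assumed, because the documents do not give it: correlation r between the 12-week RMDQ and the imputation predictors, shown at 0, 0.5 and 0.7.

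**Formulas (Rubin's rules, MIANALYZE default degrees of freedom).**
- Within-imputation variance: W = 4.5²(1/160 + 1/117) = 0.2996.
- Total variance with unlimited imputations: T = 4.5²[r²(1/160 + 1/117) + (1 − r²)(1/128 + 1/93.6)].
- Between-imputation variance: B = T − W. Fraction of missing information: B/T.
- Upper limit: Q + t(0.975, ν) × √(W + (1 + 1/m)b), where λ = (1 + 1/m)b / (W + (1 + 1/m)b) and ν = (m − 1)/λ². From seed to seed, Q varies with variance B/m, and b varies around B as a scaled chi-square on m − 1 degrees of freedom.

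**Numbers at r = 0.** T = 0.3745, B = 0.0749, B/T = 0.20. The pooled difference alone has seed-to-seed SD √(0.0749/5) = 0.122. The noise in b adds about as much again: √(0.172² − 0.122²) = 0.121. With b at B, ν = 4/0.2308² = 75 and the half-width is 1.992 × √0.3895 = 1.243, against 1.960 × √0.3745 = 1.200 with unlimited imputations.

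Drawing Q and b twice for each of 400,000 trials gives:

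| r | B/T | m | SD of upper limit | Mean gap between two seeds | Opposite verdicts, true difference 0 | Opposite verdicts, 0.4 | Success, true difference 0 |
|---|---|---|---|---|---|---|---|
| 0 | 0.20 | 5 | 0.172 | 0.192 | 6.1% | 10.5% | 88.3% |
| 0 | 0.20 | 20 | 0.074 | 0.084 | 2.4% | 4.5% | 90.0% |
| 0 | 0.20 | 50 | 0.046 | 0.052 | 1.4% | 2.7% | 90.3% |
| 0.5 | 0.16 | 5 | 0.140 | 0.157 | 4.5% | 8.3% | 90.4% |
| 0.5 | 0.16 | 20 | 0.062 | 0.070 | 1.8% | 3.6% | 91.6% |
| 0.5 | 0.16 | 50 | 0.039 | 0.044 | 1.1% | 2.3% | 91.7% |
| 0.7 | 0.11 | 5 | 0.107 | 0.120 | 3.0% | 6.2% | 92.3% |
| 0.7 | 0.11 | 20 | 0.049 | 0.055 | 1.3% | 2.8% | 92.9% |
| 0.7 | 0.11 | 50 | 0.031 | 0.035 | 0.8% | 1.7% | 93.0% |

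The power cost of 5 sets against 50 is 90.3 − 88.3 = 2.0, 91.7 − 90.4 = 1.3 and 93.0 − 92.3 = 0.7 percentage points.

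**Type I error.** At a true difference of 2, false non-inferiority is 2.5% with 5, 20 or 50 sets, at every r.

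**Cross-check.** A full simulation that re-imputed the same trial data under 30–40 seeds gave SDs of 0.177, 0.141 and 0.109 at m = 5. With baseline adjustment in the analysis it gave 0.151 at r = 0.5 and 0.124 at r = 0.7.

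**How often the margin is close.** At a true difference of 0, the upper limit lies within 0.2 of 2 in about 9–11% of trials. The flips come from trials near the margin.

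**The case against.** Five points can be made for the plan.

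1. *The trigger speaks of a covariate.* Read literally, the five sets apply to covariates only, and the 12-week comparison, which names no covariates, is untouched. But the same paragraph discusses data missing at 3 and 6 months and says that the imputation yields the treatment effect and its confidence limit. The documents define covariates as baseline measurements. Imputing the outcome is therefore the natural reading, though it remains a reading and the text should settle it.
2. *Imputation is conditional.* At 15% missing or less, the rule does not operate. This stands. The point applies because the plan itself expects 20%.
3. *Zero correlation is pessimistic.* Baseline RMDQ is the same 24-item scale, and some patients who miss month 3 will have month 6. This also stands: at r of 0.5–0.7, flips at a true difference of 0 are about 3–4.5% and the power loss is about 1 point.
4. *The mixed model on the 3- and 6-month scores is a check that needs no seed.* Fitted by likelihood, it needs no imputed outcomes. But it is an additional analysis; the stated decision rests on the 12-week limit.
5. *Twenty sets would do most of the work.* True: 20 sets already remove more than half of the noise. Fifty reduces it further at no real cost.

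A reader might infer that five imputations make the test invalid, or that the seed rather than the patients decides the trial. The calculations do not support either. The false-positive rate holds at 2.5%, and seed noise of 0.11–0.17 is small beside the sampling standard error of the difference, √T = 0.58–0.61.

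**Conclusion.** The point holds as one of reproducibility and a small loss of power. With more than 15% of RMDQ outcomes missing and imputed, at the planned 20%, five sets leave the deciding limit with a seed-to-seed SD of about 0.11–0.17 points. Opposite verdicts from two runs occur in about 3–6% of trials at a true difference of 0 and about 6–11% at 0.4. Power at a true difference of 0 is about 1–2 percentage points below that with 50 sets. A flip needs an upper limit already within a few tenths of 2.

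The figures rest on an assumed correlation of 0 to 0.7, missingness at random, equal 20% loss in both arms, and a single analysis set. They do not model the joint requirement for the per-protocol set. Validity is not in question. This is a free improvement.

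**What to change.** In protocol D.9 (Approach to Missing Data) and the SAP (Handling Missing Data):

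- Replace five imputed sets with at least 50. The SD of the upper limit then falls to about 0.03–0.05, and opposite verdicts to about 1–1.5% at a true difference of 0 and 2–3% at 0.4.
- State the random seed in the SAP before the data are unblinded. A seed alone would make the run repeatable but would leave the noise and the power loss, so it goes with the larger number of sets and does not replace it.
- Reword the trigger so that it names the RMDQ outcome as well as covariates.

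The cost is about one line of text in each document and seconds of computing. There is no statistical downside.
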